#### **Stopping Rules:**

#### **Individual Subject Stopping Rule:**

Subjects with an sUA level >6 mg/dL at 2 consecutive study visits beginning with the Week 2 Visit (not including post-infusion samples) will discontinue treatment and remain in the study.

KRYSTEXXA IND: 010122

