#### Statistical Analysis on Efficacy Parameters

The efficacy analysis will be performed using the modified intention-to-treat (mITT) population, defined as all enrolled subjects who received ≥1 dose of pegloticase. The proportion of Month 6 responders will be summarized, along with a 95% confidence interval for the proportion. The proportion of Month 3 and overall (Months 3 and 6 combined) responders will be analyzed similarly.

A subject will be declared a non-responder if the subject had sUA level > 6 mg/dL at 2 consecutive study visits beginning with the Week 2 Visit. In addition, a subject who withdraws from study treatment for any reason after the first dose of pegloticase in the Pegloticase + IMM Period and prior to Month 6 (for the primary endpoint) or Month 3 (for the secondary endpoint) will be considered a non-responder if sUA values are not collected at the planned time points.

Swollen/tender joint counts, HAQ scores, patient and physician global assessment scores, subject assessment of joint pain scores, and mean sUA changes from baseline and values at baseline and each visit will be summarized with descriptive statistics. The proportion of subjects achieving 20%, 50%, or 70% improvement based on gout chronic response criteria will be summarized. For subjects with DECT scans, changes from baseline and values at Weeks 24, 36 and 52 for urate volume will be summarized with descriptive statistics.

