### 9.3.3.1.1 Study considerations for subjects ending pegloticase infusions prior to 52 weeks

 Methotrexate, along with folic acid, will be discontinued at the time of cessation of pegloticase infusions prior to Week 52.

Protocol: HZNP-KRY-201

KRYSTEXXA IND: 010122

Version 3.0, Adminstrative Change 1

 All subjects will complete the End of Pegloticase Infusions Visit and will remain on study through week 52 regardless of whether they stop infusions due to sUA stopping rules or other reason (e.g. withdrawal of consent for pegloticase infusions).

- Subjects are encouraged to continue to participate in all visits through the end of the study. Subjects are especially encouraged to complete study visits at the study site during key efficacy and safety collections at Weeks 10, 12, 14, 20, 22, 24, 32, 34, 36, 48, 50 and 52, so that sUA labs and other key assessments can be completed. Subjects who have stopped infusions, may complete the other study visits in person or via telephone to collect AEs, conmeds and gout flare information.
- Activities related to pre/post infusion monitoring or medication dispensation will not be completed once a subject has stopped pegloticase infusions. These activities include:
  - o MTX compliance/reconciliation
  - Infusion reaction prophylaxis
  - IR prophylaxis compliance
  - Folic acid compliance
  - Pegloticase infusion
  - Pegloticase PK sampling
  - Pre-infusion MTX Polyglutamate sampling
  - o MTX drug/dispensation related items

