### 9.3.3.2 Removal of Subjects From Study

In addition to completion of therapy and designated study visits through Week 52, the reason for discontinuation from the study should be recorded on the eCRF using 1 of the following categories:

- Lost to Follow-up. The subject does not return to the clinic for scheduled assessments, and does not respond to the site's attempts to contact the subject.
- Withdrawal of Consent. The subject withdraws from the study. The clinical site should attempt to determine the underlying reason for the withdrawal and document it on the eCRF; (i.e. AE, voluntary withdraw), Specify.
- Study Terminated by Sponsor. The Sponsor, IRB, or regulatory agency terminates the study.

KRYSTEXXA IND: 010122

Death.

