# 9.5.6.3 End of Pegloticase Infusions Visit

Subjects who end pegloticase infusions prior to Week 52 will complete the End of Pegloticase Infusions Visit procedures following their final infusion. Subjects should continue to participate in all visits through the end of the study. Subjects must complete selected study visits at the study site during key efficacy and safety collections Weeks 10, 12, 14, 20, 22, 24, 32, 34, 36, 48, 50 and 52, so that sUA labs and other key assessments can be completed. Visits between these key efficacy and safety collection visits, for subjects who have stopped infusions, may be completed in person or via a telephone visit option to collect AEs, concomitant medication and gout flare information (See 9.3.3.1.1).

The following procedures will be completed at the End of Pegloticase Visit:

- Investigator Assessment of Clinical Status.
- Document gout flares and intensity.
- Perform a targeted physical examination should include heart, lungs and abdominal exam and joint and skin evaluation and assessment of AEs. Any finding will be recorded as an AE.
- Record vital signs (blood pressure, respiratory rate, temperature, and heart rate including the measurement of weight. (see Section 9.5.4.4).
- Collect swollen/tender joint counts; administer HAQ; and record patient and physician global assessments and joint pain assessment responses.
- Assessment of Tophi.
- Assess MTX compliance.
- Ask Yes/No question regarding folic acid, gout flare prophylaxis, and IR prophylaxis compliance.

Horizon Therapeutics Ireland DAC Date: 01 April 2020

Protocol: HZNP-KRY-201 Version 3.0, Administrative Change 1

KRYSTEXXA IND: 010122

 Obtain a urine sample from all females of childbearing potential for performance of a pregnancy test.

- Obtain blood samples for hematology and clinical chemistry analysis.
- Obtain a urine sample for uric acid:creatinine ratio.
- Obtain blood samples for pegloticase PK analysis.
- Obtain blood samples for anti-PEG and anti-uricase IgG antibodies.
- Obtain a blood sample (1 sample) for measurement of sUA.
- Inquire about AEs and concomitant medication use.
- Perform DECT (if applicable). DECT may be completed within +/- 5 days of the scheduled visit. Subjects who end pegloticase infusions prior to Week 52 should follow the scheduled timepoints but avoid a repeat DECT scan within 6 weeks of a prior scan.

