#### 9.6.5.1 Primary and Secondary Endpoint Analysis

The primary efficacy endpoint is the proportion of responders during Month 6. A responder is defined as a subject for whom the proportion of time that the sUA-time curve is <6 mg/dL during Month 6 (Weeks 20, 22, and 24) is at least 80%. The proportion of time that the sUA level is below 6 mg/dL is defined as the ratio of the time during which the sUA level remains below 6 mg/dL (using linear interpolation, if necessary) to the entire time interval during Month 6. The proportion of responders will be summarized, along with a 95% exact (Clopper-Pearson) confidence interval for the proportion. The proportion of Month 3, overall (Months 3 and Month 6 combined), and 5 mg/dL responders (during Month 3, Month 6, and overall) will be summarized similarly.

Protocol: HZNP-KRY-201

KRYSTEXXA IND: 010122

Version 3.0, Administrative Change 1

A subject will be declared a non-responder if the subject had sUA level > 6 mg/dL at 2 consecutive study visits beginning with the Week 2 Visit. In addition, a subject who withdraws from the study for any reason (other than stopping rule) after the first dose of pegloticase in the pegloticase + IMM Period and prior to or during Month 6 (for the primary endpoint) or Months 3 or 6 (for the secondary endpoints) will be considered a non-responder if sUA values are not collected at planned timepoints.

sUA will be summarized at each visit and change from baseline to each visit with descriptive statistics.

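### The non-response rule for the primary endpoint is tied to stopping study treatment in the Synopsis but to leaving the study in Section 9.6.5.1, so the same subject can be scored two ways

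*Protocol*

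**What the plan says.** The rule appears twice in the current protocol.

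- Synopsis, Statistical Analysis on Efficacy Parameters: it applies to "a subject who withdraws from study treatment for any reason after the first dose of pegloticase", with the window "prior to Month 6 (for the primary endpoint) or Month 3 (for the secondary endpoint".
- Section 9.6.5.1: it applies to "a subject who withdraws from the study for any reason (other than stopping rule) after the first dose of pegloticase", with the window "prior to or during Month 6 (for the primary endpoint) or Months 3 or 6 (for the secondary endpoints".

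In both places the consequence is non-response, and only if sUA was not collected when planned. Both texts also make anyone with sUA above 6 mg/dL at two consecutive visits from Week 2 a non-responder.

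Section 9.6.5.1 alone defines the calculation: time below 6 mg/dL, with linear interpolation where needed, divided by the whole of the Month 6 interval. A responder needs at least 80%.

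The protocol separates the two kinds of withdrawal. Section 9.3.3.1 lists reasons for ending pegloticase. Section 9.3.3.2 has its own list, under which "the reason for discontinuation from the study should be recorded on the eCRF using 1 of the following categories". Sections 9.3.3 and 9.3.3.1.1 keep subjects who stop pegloticase on study to Week 52. Subjects who meet the sUA stopping rule "will discontinue treatment and remain in the study".

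On the draws after treatment ends, Section 9.3.3.1.1 says "Subjects are especially encouraged to complete study visits at the study site during key efficacy and safety collections", while Section 9.5.6.3 says "Subjects must complete selected study visits at the study site during key efficacy and safety collections".

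**The concern.** This rule decides who counts in the numerator of the primary endpoint. Because stopping pegloticase is not leaving the study, the two triggers are not synonyms. The Synopsis reaches a subject who stops treatment and stays on study; Section 9.6.5.1 does not. The gap concerns a group the protocol deliberately creates, namely treatment stoppers who are kept for follow-up. Missed draws in that group are foreseeable, because the protocol is inconsistent on whether the key-week visits are required. Two analysts working from the same data and the same protocol could report different response rates.

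**Working it through.** **The plan's own figure.** Section 9.6.9 gives a benchmark of 10/13 against 43.5%, with a lower 95% bound of about 46%. The exact binomial tail P(X ≥ 10 | n = 13, p = 0.435) is 0.0155. The Clopper-Pearson interval for 10/13 is 46.2% to 95.0%. The stated figure reproduces.

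**The two rules side by side.**

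| | Synopsis | Section 9.6.5.1 |
|---|---|---|
| Trigger | stops study treatment | leaves the study, stopping rule excepted |
| Window, primary | before Month 6 | before or during Month 6 |
| Window, secondary | before Month 3 | Months 3 or 6 |
| Condition | planned sUA missing | planned sUA missing |

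**Case 1: treatment stopped for an adverse event after Week 18, subject stays on study, sUA below 6 at Weeks 20 and 24, Week 22 missed, never two consecutive values above 6.**
- Synopsis: the trigger is met before Month 6 and a planned value is missing. Non-responder, if one missed draw is enough.
- Section 9.6.5.1: the subject has not left the study, so the rule does not apply. A straight line between two values below 6 stays below 6, so 28 of 28 days = 100%, which is at least 80%. Responder.

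**Case 2: as Case 1, but none of the three Month 6 draws was taken.**
- Synopsis: non-responder, whether the condition means any or all planned values missing.
- Section 9.6.5.1: the withdrawal rule still does not apply. The result is 0 of 28 days if nothing bridges the gap, and up to 28 of 28 if values on either side of the month are joined. The section does not say which.

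**Case 3: subject leaves the study after Week 22, sUA below 6 at Weeks 20 and 22, no later draw.**
- Section 9.6.5.1: non-responder by rule.
- Synopsis: no withdrawal rule applies, because withdrawal was not before Month 6. The only stated denominator, the full interval, gives 14/28 = 50%, which is below 80%. Non-responder.

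**Case 4: overall endpoint, subject leaves after Week 14 with all Month 3 values below 6.**
- Section 9.6.5.1: non-responder by rule.
- Synopsis: no rule applies. The same approach gives 28/56 = 50%. Non-responder.

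The trigger can therefore change a classification. The differing windows do not do so by themselves in Cases 3 and 4.

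**Effect of one subject.** 100/12 = 8.3, 100/13 = 7.7 and 100/16 = 6.3 percentage points.

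| Responders | Rate | 95% Clopper-Pearson |
|---|---|---|
| 9/13 | 69.2% | 38.6% to 90.9% |
| 10/13 | 76.9% | 46.2% to 95.0% |
| 11/16 | 68.8% | 41.3% to 89.0% |
| 12/16 | 75.0% | 47.6% to 92.7% |

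**The case against.** The best case for leaving the text alone is that the conflict rarely matters. With complete Month 6 sUA the two texts give the same count. Case 1 needs several things together: a stop for a reason other than sUA before Month 6, continued participation, a missed draw that interpolation can bridge, and sUA below 6 around it while off both pegloticase and methotrexate. It also needs the Synopsis condition to mean any missed draw. If it means that all must be missing, Case 1 is a responder under both texts.

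These points limit the size but do not remove the conflict. If all draws must be missing, Case 2 is still settled by the Synopsis and left open by Section 9.6.5.1. Nor can the matter simply be left to the statistical analysis plan: the protocol fixes the rule twice, and a plan that follows one version departs from the other.

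The exception for the stopping rule in Section 9.6.5.1 changes no count, because the preceding sentence already makes those subjects non-responders. It is misplaced rather than harmful: that rule ends treatment, and it is not among the Section 9.3.3.2 reasons for leaving the study.

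A reader might also infer that the plan wrongly credits response produced by another urate-lowering drug, since the restriction in Section 9.4.9 runs only to the end of pegloticase and methotrexate treatment. The documents do not support calling that an error. How to score such values is a choice of estimand that is commonly left to the analysis plan.

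**Conclusion.** The two statements of the rule conflict on the trigger and should be reconciled. The finding rests on the protocol's own separation of stopping treatment from leaving the study. Case 1 additionally assumes that one missed planned draw is enough under the Synopsis; Case 2 does not.

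The likely effect is zero or one subject, an assumption because the documents give no frequency. One subject is worth 6.3 to 8.3 points at the planned 12 to 16.

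Two stronger conclusions are tempting. The first is that the differing windows also change the count. Under the denominator in Section 9.6.5.1 they do not in the cases worked through. The second is that one subject could turn success into failure, because in both pairs above the lower bound crosses 43.5%. Section 9.6.5 says there will be no statistical testing, so the effect is on a reported proportion and its interval, not on a formal decision.

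**What to change.** Use one wording in the Synopsis and in Section 9.6.5.1. It should:

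- cover subjects who stop study treatment but remain on study as well as those who leave the study;
- apply to events before or during the month being assessed, and to both Months 3 and 6 for the overall endpoint;
- state whether one missed planned draw is enough or all must be missing;
- drop the redundant exception for the stopping rule.

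Reconcile Section 9.3.3.1.1 with Section 9.5.6.3 on whether the key-week visits and their sUA draws are required after infusions end.

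Optionally, and not to correct an error, say how sUA taken after the start of another urate-lowering drug is scored.

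The cost is wording only. The downside is that the reported response rate may be slightly lower.

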### 9.6.5.2 Exploratory Endpoint Analysis

Swollen/tender joint counts, HAQ scores, patient and physician global assessment scores, and subject assessment of joint pain scores will be summarized at each visit along with changes from baseline using descriptive statistics.

The proportion of subjects achieving 20%, 50%, or 70% improvement based on gout chronic response criteria will be calculated based on improvement in each of the components and summarized at Weeks 14, 24, 36 and 52. The proportion of responders at Month 9 and Month 12 will be summarized in a similar manner as the primary and secondary responder endpoints.

For subjects with DECT scans, the urate volume and bone erosion due to gout at each visit and changes from baseline will be summarized using descriptive statistics.

# 9.6.6 Pharmacokinetic and Anti-drug Antibody Analysis

Concentrations of pegloticase and MTX polyglutamate (as appropriate) will be summarized using descriptive statistics for the PK population. Details will be provided in a separate PK analysis plan.

Incidence of anti-drug antibodies and titer levels will be summarized.

#### 9.6.7 Safety Analysis

Treatment-emergent AEs (TEAEs) during the Run-In period are defined as events with an onset date on or after the first dose of MTX through the first pegloticase infusion, or 30 days after the last dose of MTX for subjects who do not receive pegloticase. TEAEs during the Pegloticase + IMM Period are defined as events that occur after the start of the first pegloticase infusion through 30 days after the last dose of pegloticase and/or MTX (whichever is later). TEAEs during the MTX Run-in Period will be summarized with the ITT population, and TEAEs during the Pegloticase + IMM Period will be summarized with both the ITT and mITT populations. TEAEs during any period (MTX Run-in Period or Pegloticase + IMM Period) will be summarized for the mITT population. AEs that occur more than 30 days after the last dose of pegloticase and/or MTX through the 6 month follow-up visit will also be summarized. The number and percentage of subjects experiencing AEs will be summarized by system organ class and preferred term. Summaries by maximum severity and relationship to MTX and pegloticase

Protocol: HZNP-KRY-201

KRYSTEXXA IND: 010122

Version 3.0, Administrative Change 1

will also be provided. SAEs and AEs leading to discontinuation of MTX and pegloticase will be presented by system organ class and preferred term.

Incidence of IRs, gout flares, and other AEs of special interest will be summarized.

Laboratory test results, including urine uric acid:creatinine ratio, will be summarized by study visit and change from baseline. Shift tables for laboratory parameters by Common Terminology Criteria for Adverse Events grade will be presented. Laboratory test results will also be classified relative to the normal reference range (normal, low, or high).

Vital signs, including blood pressure, respiratory rate, temperature, and heart rate, will be summarized by study visit and change from baseline.

Prior and concomitant medications will be summarized and/or included in the data listings.

Data for the MTX Run-in Period and Pegloticase + IMM Period will be summarized separately, where applicable.

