#### **Duration of Treatment and Follow-up:**

**Screening:** Completed within 2 weeks prior to the Week -4 visit

MTX Run-in Period (Week -4 through Day 1): Includes 4 weeks of MTX weekly dosing

**Pegloticase** + **IMM Period (Day 1 through Week 52)**: MTX dosed weekly and 50 weeks of pegloticase infusions visits every 2 weeks); Non-infusion visits at Weeks 1, 7 and 52.

KRYSTEXXA IND: 010122

**End of Pegloticase Infusions Visit (if applicable)**: If the subject discontinues pegloticase treatment prior to infusion Week 50, such as due to the sUA stopping rules, the subject will complete this visit within approximately 2 weeks of the last infusion. Subjects will continue study.

Week 52/End-of-study/Early Termination Visit: Week 52 or earlier if the subject withdraws consent to participate in the study.

Safety Follow-up Visits: All subjects will receive a safety follow-up phone call/e-mail/visit approximately 30 days after the last dose of pegloticase/MTX to assess if any SAE's have occurred. Subjects who receive at least one dose of MTX and are females of childbearing potential, will receive a safety follow-up phone call/e-mail/Site Visit approximately 30 days after the last dose of MTX to verify at least one ovulatory cycle has occurred after the last dose of MTX. If the subject has not ovulated, a urine pregnancy test will be performed. Subjects who receive at least one dose of MTX and are non-vasectomized males, a phone/e-mail/Site Visit inquiry will be conducted 3 months after MTX discontinuation regarding partner pregnancy (inquiry can occur during the 3 month Post Treatment Follow-up).

**3 and 6 Month Post Treatment Follow-up Visits:** All subjects will be followed for a minimum of 6 months following the last infusion, with follow-up after Week 52 as warranted.

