### **Pegloticase**

All subjects will receive pegloticase at the same dose of 8 mg administered IV every 2 weeks for a total of 26 infusions from Day 1 through Week 50, inclusive (Pegloticase + IMM Period). Subjects will not be fasting on the day of infusion and will be encouraged to have a snack or normal meal before or after the infusion. Pre-infusion sUA results must be reported by the local or central laboratory prior to pegloticase infusion (see Section 9.5.1.1).

Standardized IR prophylaxis consisting of pre-treatment with antihistamines, acetaminophen, and corticosteroids will accompany each infusion (see Section 9.4.1.3). The drug name, dose, and timing of these prophylactic medications will be recorded.

Pegloticase will be administered as an admixture of 8 mg in 250 mL of 0.45% or 0.9% Sodium Chloride Injection, USP for IV infusion by gravity feed or infusion pump. Pegloticase will not be administered as an IV push or bolus.

In a patent IV site, using tubing with no in-line filter, the pegloticase preparation will be infused over approximately  $120 \pm 15$  minutes while the subject is under close observation for any signs of distress. If an in-line filter is used, it should be  $0.2~\mu m$  or larger. At the end of the infusion, the IV line will be flushed with 10~mL of normal saline to ensure the full dose is administered. The date and time of infusion start and stop (inclusive of the IV flush) will be recorded.

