### **Infusion Reaction**

An IR will be defined as any infusion-related AE or cluster of temporally-related AEs, not attributable to another cause, which occur during the pegloticase infusion and for 1 hour post infusion. Other AEs that occur outside of the 1-hour window following the infusion may also be categorized as an IR at the Principal Investigator's discretion. Signs and symptoms of the IR and treatments administered will be documented in the medical record and in the eCRF.

Examples of AEs not considered possible IRs include, but are not limited to: laboratory abnormalities that are unlikely to have occurred during or within 1 hour following the infusion (e.g., anemia), gout flares, most infectious diseases, or the recurrence or worsening of a known chronic medical problem identified in the subject's medical history.

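### The run-in and Pegloticase + IMM windows for treatment-emergent adverse events overlap during the first infusion, so an event then falls in both period tables

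*Protocol*

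**What the plan says.** Protocol 9.6.7 sets two windows for TEAEs. The run-in window takes in "events with an onset date on or after the first dose of MTX through the first pegloticase infusion"; for subjects who never receive pegloticase it ends 30 days after the last methotrexate dose instead. The Pegloticase + IMM window takes in "events that occur after the start of the first pegloticase infusion through 30 days after the last dose" of pegloticase or methotrexate, whichever is later.

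The tables follow these windows. For the run-in, "TEAEs during the MTX Run-in Period will be summarized with the ITT population". Events of the later period are tabulated twice, once for each of the ITT and mITT populations. A further table for either period uses the mITT population. The counting unit is the subject, by system organ class and preferred term. The same section says that the two periods are to be summarized separately where applicable. Infusion reactions and other events of special interest also get their own incidence summary, for which no period is stated.

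The synopsis section on duration of treatment gives the run-in as "MTX Run-in Period (Week -4 through Day 1): Includes 4 weeks of MTX weekly dosing" and starts the Pegloticase + IMM Period on Day 1, so the infusion day belongs to both. Under the infusion-reaction heading in 9.5.4.1.1.5, infusion reactions are infusion-related events "which occur during the pegloticase infusion and for 1 hour post infusion"; later events may be added at the investigator's discretion.

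**The concern.** The run-in table covers the four weeks on methotrexate before any pegloticase. A reaction during infusion 1 is an event under pegloticase exposure, yet it satisfies the run-in definition as written. A programmer who follows 9.6.7 exactly would place it in the run-in table and again in the Pegloticase + IMM table. That defeats the stated aim of summarizing the periods separately.

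Infusion reactions and anaphylaxis are named safety endpoints in 9.6.1.5, and in a study of 12-16 subjects one subject visibly moves a percentage. Section 9.6.8 also provides for regular safety summaries during the study, so the ambiguity would arise before the final analysis.

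**Working it through.** No planned figure rests on these windows, so the check compares them as intervals on Day 1.

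**Inputs**
- Run-in window, upper end (9.6.7): through the first infusion, stated in terms of onset date.
- Pegloticase + IMM window, lower end (9.6.7): "events that occur after the start of the first pegloticase infusion".
- Infusion length (9.4.6.3.1.2, Pegloticase): "the pegloticase preparation will be infused over approximately" 120 ± 15 minutes, that is 105 to 135 minutes.
- Infusion-reaction window (9.5.4.1.1.5): the infusion plus 1 hour.
- Planned size (9.6.9): approximately 12-16 subjects; its worked example uses 13.

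**Classification.** Let t be minutes from the start of the first infusion, with a nominal end at t = 120. The pegloticase window is t > 0. The run-in window is t ≤ 120 if applied by clock time, or all of Day 1 if applied by onset date.

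| Onset on Day 1 | Pegloticase + IMM window | Run-in, by clock time | Run-in, by onset date |
|---|---|---|---|
| t = −60 | no | yes | yes |
| t = 1, 60, 119 | yes | yes | yes |
| t = 121, 150, 180 | yes | no | yes |

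- Onset during the infusion meets both definitions on either reading.
- Onset after the infusion, including the 1-hour reaction window, meets both only if the run-in window is applied by date.
- Onset before the infusion is run-in only.

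The overlap is therefore at least the infusion itself (105 to 135 minutes) and at most the rest of Day 1 from infusion start.

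**Effect on the tables.** The ITT population is everyone who takes a dose of methotrexate (9.6.2). It thus contains every subject who goes on to pegloticase, and an overlapping event enters both period tables. The any-period mITT table counts a subject once, whichever window the event falls in.

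**Size in the run-in table.** One misassigned subject adds at most 1/N to a row, where N is the ITT count. The addition is zero if that subject is already counted in the row.
- N = 16: 1/16 = 6.3%
- N = 13: 1/13 = 7.7%
- N = 12: 1/12 = 8.3%

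Subjects who take methotrexate but fail the run-in (9.3.4.3) also belong to the ITT population. The Schedule of Assessments marks enrollment at Day 1. If 12-16 counts only enrolled subjects and k others fail the run-in after a dose, the shift becomes 1/(N + k). For example, 12 enrolled plus one failure gives 1/13 = 7.7% instead of 8.3%.

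**After the change.** If the run-in window is t < 0, no value of t satisfies both definitions.

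**The case against.** The best reply is that this is a loose boundary phrase. Because 9.6.7 wants the periods summarized separately, *through* the first infusion can be read as up to its start, and the SAP may say so. That reading would remove the overlap, but the protocol does not state it. The protocol itself fixes both windows, so a SAP that followed them would inherit the conflict and one that cured it would depart from them.

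The second reply is that a misplaced reaction would still be recognizable. Each event is assessed for its relationship to methotrexate and to pegloticase (9.5.4.1.4) and summarized that way, and events of special interest have their own eCRF. This stands as mitigation: a reader of the full report could trace the event. It does not correct the run-in table.

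Four stronger readings are tempting and are not supported:
- **Reactions are counted twice throughout.** They appear once in each period table. The any-period table counts subjects, and the infusion-reaction incidence is not stated by period.
- **Every Day 1 event falls in both windows.** The pegloticase window opens at a point in time, so events before the infusion do not meet it.
- **The safety objective calls for separating the two drugs.** The objective and 9.6.1.5 speak of the overall profile and of events potentially attributed to the combination.
- **The 26% Phase 3 infusion-reaction rate in 7.1.1 measures the problem** (0.26 × 13 = 3.4 subjects). That rate is not specific to the first infusion. Section 7.2 says reactions were more common in subjects whose sUA rose after an initial response to the first 1 or 2 infusions.

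**Conclusion.** The two definitions in 9.6.7 overlap, and following them as written puts events with onset during the first infusion into the run-in table as well as the Pegloticase + IMM table. If the run-in window is applied by onset date, the overlap extends to later Day 1 events after infusion start.

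The shift is up to about 6 to 8 percentage points per misassigned subject. This assumes an ITT count of 12-16 and a subject not already counted in that row; run-in failures in the ITT population would make it smaller. How many subjects this would affect cannot be estimated, because the protocol gives no first-infusion reaction rate.

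The primary and secondary endpoints, the sample-size statement and the stopping rule are untouched. This is a rule stated wrongly, with a limited effect on the safety tables, and it is worth correcting before the first safety summary.

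**What to change.** In 9.6.7, end the run-in TEAE window immediately before the start date and time of the first pegloticase infusion. Open the Pegloticase + IMM window at or after that same moment, so that the two meet without overlap or gap. Add that Day 1 events whose onset time is missing, or cannot be placed before the infusion, are assigned to the Pegloticase + IMM Period. Carry the same wording into the SAP.

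The cost is a sentence or two, with no change to visits or dosing. The infusion start time is already recorded (9.4.6.3.1.2 and 9.4.10). Adverse-event onset time may not be: Section 10 requires only start and stop dates as a minimum, which is why the assignment rule is needed.

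The rule has a small downside. A few Day 1 events that in fact preceded the infusion but have no recorded time may be assigned to the pegloticase period. That could include events after a methotrexate dose given that morning, which 9.5.6.2.1 allows.
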